Participants in phase 1 (N = 25) and phase 2 (N=60) will be boys and girls (ages 13-19 yrs) who have high mood instability scores, at least one parent with a history of BD or MDD, and at least one parent rated high in Perceived Criticism, a 1-10 child- and parent-rated scale that is a proxy measure for expressed emotion (EE). Each family will receive 12 FFT sessions in 18 weeks, with assessments of EE, mood instability, and symptoms/functional outcomes at intake, mid-treatment, post-treatment (18 wks.) and follow-up (27 wks.). At study entry, all participants will be given access to the MyCoachConnect (MCC) smartphone app with an interactive voice-response (IVR) system. In phase 1, all participants (adolescents and parents) will receive FFT and the fully functional MyCoachConnect (MCC) app. In phase 2, participants will be randomly assigned in a 1:1 split to:

(1) **FFT with the full MCC app (FFT-MCC)**, consisting of instructions for daily mood, sleep and family functioning ratings, how to use FFT skills (e.g., symptom tracking, active listening, problem-solving), and how to log efforts to practice these skills; instructional videotapes showing how the skills are used in practice; and weekly and standard interval (every 9 week) assessments completed by the participant on the app. The clinical provider, via the MCC app, will send tailored alerts to parents and youth about mood management strategies and pertinent communication skills for resolving conflicts, which they can practice between sessions. All participants (adolescents, parents) will be instructed to call the automated voice system twice per week and leave a 3-5 minute speech sample surveying how they are doing and how they are getting along with their child (or parent).

(2) **FFT with the Assessment App (FFT-ASSESS)**, the same 12 sessions of FFT will be given, but with a scaled-down version of the app consisting of weekly questionnaires to be rated and call-in instructions, plus standard interval (every 9 week) questionnaire assessments. There will be no educational or skill-oriented coaching of participants by clinicians via the app. However, families will still receive the standardized course of 12 sessions/ 4 months of FFT, which is more than families with children with mood disorders ordinarily receive in the community.

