The FFT protocol for early-onset youth, to be given in both conditions, consists of 12 one-hour family sessions (8 weekly, 4 biweekly), usually completed within 18 weeks. (The full FFT manual and handouts are accessible through www.semel.ucla.edu/champ/downloads). The system for rating fidelity using the Therapy Competence and Adherence Scales consists of 11 items (e.g., communication training, problem-solving) rated by an independent rater from (1) no fidelity (e.g., therapist did not use this strategy) to (7) excellent fidelity (therapist used this strategy frequently and effectively) (Marvin, [name], O'Brien, & Cannon, 2014).

Family engagement (sessions 1 and 2). The clinician schedules an initial meeting with the teen and available family members (usually parents or siblings), and reviews the stages of FFT and use of the MCC app: (1) how to call the server and provide a speech sample; (2) how to respond to questionnaire items; and (3) what to expect in terms of weekly reminders. Treatment goals from the adolescent's, parents', and clinician's viewpoints are clarified.

Psychoeducation (sessions 2-5) assists the family in recognizing early signs of mood episodes in the adolescent, and distinguishing mood instability from developmentally appropriate emotional reactivity. A major goal of this phase is for family members to understand that the youth's aversive behavior may be due to a biologically-based illness, and is not always under his/her control. Adolescents and parents/siblings are encouraged to identify triggers for their mood swings (e.g., sleep/wake changes; negative family interactions). Adolescents are assisted in developing their own mood management plan, which usually includes (a) monitoring moods and sleep/wake rhythms, (b) learning to anticipate factors that destabilize mood, and (c) a list of "go-to" emotion regulation strategies to arrest mood escalation or deterioration (e.g., mindful breathing, behavioral activation).

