MCC Intervention Support: Individuals in FFT-MCC will have access to an interactive, mobile intervention via MCC. This intervention consists of supportive text messages sent to participants (both youth and parents) in between FFT sessions with content based on material covered that week and tailored by FFT providers, based on the participants' needs.

The app will send text messages with information related to family engagement, psychoeducation and skills training as the family transitions from one of these treatment modules to the next. Individuals can also initiate contact with the mobile app by clicking buttons to explore skills and relevant didactic material in more depth, and to obtain coaching related to responding in specific family conflicts (e.g., when anticipating a conflict, reminders about active listening and specific negotiation skills). The MCC app can be used on-demand (e.g., when an adolescent has worsening symptoms) by both parents and youth. The app will send push notifications to indicate whether or not the participant or parent have recorded use of a skill for that week.

Rewards. Participants are assigned an emoji avatar when they enter the study. They can “level up” each week and receive other emoji rewards by completing daily mood ratings, weekly app questionnaires, recording at least one voice message per week, and recording at least two skills per week (e.g., having a family meeting and practicing active listening).

The FFT Assessment Only App (FFT-Assess)

This version of the app, given in conjunction with the same 12-session FFT given in the FFT-MCC condition, differs in one important way: it only captures the online symptom/social functioning and voice assessments, but does not contain the didactic psychoeducational or skill-oriented information contained in the FFT-MCC app nor the reminders to practice skills between sessions. There will be no emoji rewards for completing the weekly assessments of mood states, family functioning, sleep, or stress (although all participants receive compensation for completing research measures, as described below). Participants are reminded to complete the weekly questionnaires and leave voice messages in the interactive voice portion of the app.

Provider Feedback and Tailoring

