Lexical features: Using the transcriptions, we extract several lexical features to use as inputs for analysis. We plan to extract features that are similar to those extracted previously. These include several overlapping methods containing affective features, including SentiWordNet, Affective Norms of English Words (ANEW), and Linguistic Inquiry and Word Count (LIWC). LIWC is a broad and commonly used feature set that contains features including metrics of word usage (such as total count, words per sentence, count of parts of speech) and measures of word norms across multiple domains of word meaning including social, cognitive processes, perceptual processes, biological process, time orientation and others. Finally, we will extract simple statistics of the word norms: average, minimum, maximum and standard deviation.

Acoustic features: Acoustic features of speech have been shown to be correlated with several mental health ratings including depression and mania. We will implement methods used previously by our group based on prior reports¹⁵, including measures of pitch, intonation, vocal formants, fundamental frequency, and inter-word pause length.

PROTECTION of HUMAN SUBJECTS

Potential Risks

This study will be of minimal risk to participants. There is a low risk of harm to patients receiving psychoeducation or family skills training. Prior studies have demonstrated the easy tolerability and efficacy of FFT for adults and children with bipolar disorder, children and adolescents at high risk for bipolar disorder, children with depression, and adolescents/young adults at high risk for psychosis (for review, see [name] & Chung, 2016). This study has no manipulations of drug treatments. Pharmacotherapy is not required and when parents and children opt for it, they will be referred to psychiatrists in the UCLA outpatient services, other community clinics, or if they prefer, their own chosen providers. There is no additional risk conveyed by the more vs. less intensive MCC augmentation.

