Children and parents may at times feel inconvenienced by the time required to complete the questionnaires, although the MCC platform will reduce the amount of time they spend on these measures. Participants may at times experience sadness or discomfort when discussing family issues, personal problems, or psychiatric symptoms, but no more than they would if they took part in psychotherapy or pharmacotherapy sessions in the community. In our pilot work, several participants told us that the open speech sample format of the MCC (e.g., “talk for a few minutes about how things are going this week”) is therapeutic in itself.

Discussing the adolescent’s psychiatric problems may at times be upsetting to the adolescent or family. If these reactions occur, the research staff, all of whom are well-trained and supervised by an attending psychologist or psychiatrist, will offer the participants emotional support and validation. Participants will also be informed that they can receive and follow-up on referrals for counseling outside of the study at any time, although they may have to be discontinued from the protocol. They can receive clinical services within the CHAMP clinic regardless of whether they participate in the study.

The children recruited for this study will have high levels of mood disturbance and mood instability. Children with significant mood variability have an increased risk of school failure, substance abuse, suicidal ideation or actions, and psychiatric hospitalizations compare to children without mood instability (Marwaha et al., 2014). The rate of hospitalization among children and adolescents with bipolar spectrum disorders is approximately 13% in one year (Goldstein et al.,

2009). ***There is no reason to suspect that rates of these illness complications will be higher if the child receives treatment in the study instead of a community treatment setting.*** Because of the psychosocial protocols administered in this study, the availability of between-session communication for the adolescent and parent provided by the app, and the referral to good practice pharmacotherapy, rates of adverse events associated with the disorder may be lower than if patients were treated in the community. Nonetheless, the independent evaluator who administers the standard interval assessments will track all adverse events that occurred during a study interval – whether study related or not - using an **Adverse Events Form** developed in our prior studies.

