We will follow protocols implemented in our prior studies with MCC speech samples. Voice samples submitted by participants will be reviewed promptly (usually within 24 hours) by study staff and transcribed. We will always have a clinician (psychiatrist or psychologist with training in assessment and management of suicidal behavior) available for study staff to contact when they are concerned about the content of a participant's speech samples. This will usually be one of the PIs ([name] or [name]) but may also include other study PhD or MD clinicians as needed. If participants report thoughts or actions related to self-harm – either in voice samples or on daily or weekly questionnaires - study clinicians will be contacted by study staff to review the reports. The clinician will then determine, using clinical best practices, what the subsequent course of action should be. If an elevated risk of suicide is evident, the clinician will contact the participant and/or family to discuss more intensive treatment options, such as inpatient care or partial hospitalization. Often, this process requires having one or more emergency treatment sessions. If there is continued concern, the clinician will provide additional safety recommendations, contact the participant's other providers, and refer to emergency services as needed. If the risk is lower, the family clinician will address risk factors related to suicidal ideation in their weekly family therapy sessions, or offer referrals to individual therapy should the participant want them.

Availability of Ancillary Treatments

Participants who do not respond to study-based treatments may require out-of-protocol emergency or other services. These participants will be retained in the protocol whenever possible. A child who needs to be hospitalized (e.g., for suicidality) will be reentered into the protocol after hospital discharge if the child and family agree to continue participating. Family sessions will be conducted in the hospital if necessary. Children or families will not be withdrawn if they seek weekly individual psychotherapy outside of the study (for example, individual therapy, group therapy, school-based counseling).

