4. Restricting access to shared disk files through appropriate use of file permissions.
5. Printing sensitive material only when absolutely necessary. When it is necessary, project staff will ensure that an authorized person is at the printer when the sensitive material appears.
6. If it is necessary to transfer materials by mail, we will use certified mail, return receipt requested, for sensitive data or communications; and registered mail for the most sensitive data or communications.
7. Re-training staff and reviewing sensitive data inventory and data safeguards annually.
8. Reporting all serious violations of the Data Safeguarding Plan in writing to the PI, with a copy to the Privacy Resource Office.

DATA SAFETY MONITORING BOARD

This study will have a separate DSMB committee, consisting of a clinical psychiatrist or psychologist, a statistician, and a community stakeholder (e.g., a parent of a child with mood disorder). The PI has already approached several individuals at UCLA and outside UCLA who have agreed to serve on the committee. The purpose of the DSMB is to review the implementation of the human subjects protocol and help assure the safety of participants. The board will review all serious adverse events (e.g., hospitalizations, suicide attempts) and other adverse events (e.g., medication nonadherence, contact with police, school truancy) in relation to treatment phase (psychoeducation, communication skills, problem-solving skills). The DSMB will make recommendations to the NIMH and the University IRBs if it believes that participants are being endangered by the study procedures or the trial should be stopped. It will make recommendations as to ways to improve the quality of care and confidentiality of the participants. As in our prior studies, this study's DSMB will work with the PI to inspect samples of data and help assure the confidentiality, reliability, and validity of the data collection, entry and management process. The DSMB board will meet yearly (or more frequently if warranted) and receive reports from the PIs about study progress and safety issues. The Board will then issue its own reports to the UCLA IRB and the NIMH, along with suggested corrective courses of action.

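### The DSMB's adverse event review is specified by FFT phase only; neither document provides a review by randomised arm, although only the app version is randomised

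*Protocol*

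**What the plan says.** The Data Safety Monitoring Board section of the protocol's Appendix gives one axis for the board's review of serious and other adverse events: they are looked at "in relation to treatment phase (psychoeducation, communication skills, problem-solving skills". The board may recommend stopping the trial if it believes study procedures endanger participants. It meets yearly, or more often if needed, and receives its reports from the PIs.

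The named phases belong to the family therapy. The Family-Focused Therapy Protocol section opens with "The FFT protocol for early-onset youth, to be given in both conditions". The section on the assessment-only app says that this version is "given in conjunction with the same 12-session FFT given in the FFT-MCC condition, differs in one important way", namely in what the app contains. The Abstract states that in phase 2 (N = 60) "participants will be randomly assigned in a 1:1 split to" the full app or the assessment app.

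On risk, the Potential Risks section asserts: "There is no additional risk conveyed by the more vs. less intensive MCC augmentation". The same section says that the independent evaluator "will track all adverse events that occurred during a study interval", whether or not they are study related, on a dedicated form.

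The SAP describes models for depression, anxiety and functioning, and an exploratory comparison of app engagement. It contains no safety analysis.

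**The concern.** The purpose of comparative safety monitoring in a randomised trial is to see whether events fall more heavily on one arm. Here the stated axis is something both arms go through alike, so it does not separate the two app versions. The protocol nevertheless makes a statement about that difference (no added risk from the fuller app). Hypothesis 2b makes a related one: suicide risk is not expected to change more in one condition than in the other. As written, the board's review cannot check the first statement, and no SAP analysis does so after the fact.

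The phase list is also incomplete as a timeline. It names psychoeducation, communication skills and problem-solving. It leaves out the engagement phase and everything after session 12. The follow-up period is not neutral with respect to the app, because FFT-MCC participants go on receiving weekly skill reminders for 9 weeks after treatment. An event in that period has no listed phase, although the randomised difference is still in force.

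At stake is whether an imbalance in hospitalisations or suicide attempts would be put before the board routinely, or only if a member asked for it.

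**Working it through.** The documents give no safety figure to reproduce. The check is a reading of the relevant sections, followed by an illustration of scale.

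**Does any section supply a review by arm?**

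- Data Safety Monitoring Board: phase only; arm is not mentioned.
- Potential Risks: covers capture of events by the independent evaluator at each interval; no comparison by arm.
- Data management section of the Appendix: a database that will eventually hold a randomisation system and an adverse event system and pass information to the board. Arm could be retrieved, but no arm-level output is specified.
- SAP: no adverse event analysis.

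The answer is no.

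**Do the phases cover the period of app exposure?**

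Engagement occupies sessions 1 and 2, psychoeducation sessions 2 to 5, and skills training sessions 6 to 12. Treatment ends at about week 18 and follow-up runs to week 27. The uncovered follow-up is 27 − 18 = 9 weeks, or 9/27 = one third of the study, plus the start of treatment.

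**Scale (illustration only).**

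Inputs: N = 60, split 1:1, so 30 per arm; 27 weeks; and a hospitalisation rate taken from Potential Risks: "The rate of hospitalization among children and adolescents with bipolar spectrum disorders is approximately 13% in one year". That rate is for a different population from the one enrolled here, so its use is an assumption.

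- Linear: 60 × 0.13 × 27/52 = 4.05 expected hospitalisations.
- Constant hazard: 1 − (1 − 0.13)^(27/52) = 0.0698; 60 × 0.0698 = 4.2, or about 2.1 per arm.
- If the true rate were half or double 13%, the linear figure would be about 2.0 or 8.1.

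A total alone does not show the split. Eight events divided 8/30 against 0/30 (Fisher exact p = 0.005) or 4/30 against 4/30 (p = 1.0) both total 8/60. If the full app multiplied risk by k, the overall rate would rise by (1 + k)/2. For k = 2, 3, 4 and 5 this is 1.5, 2.0, 2.5 and 3.0, with no indication of which arm was responsible.

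What an arm table could show formally is limited:

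| Split (30 per arm) | Fisher exact p, two-sided |
|---|---|
| 4 vs 0 | 0.11 |
| 5 vs 0 | 0.052 |
| 6 vs 0 | 0.024 |

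Six or more events have probability 0.22 under a Poisson mean of 4.05. Exact Fisher power, with 7.0% risk in the comparison arm and two-sided alpha 0.05 (assumed), is about 4%, 20%, 44% and 69% for risk ratios of 2, 3, 4 and 5.

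**The case against.** The strongest reply is that silence is not prohibition. The protocol does not prescribe pooled tables and does not say that arm is withheld. With about 4 hospitalisations expected, the board may well review events case by case. It includes a statistician, and the planned database would let arm be retrieved on request. A reader might infer that harm from the full app would necessarily be pooled away. The documents do not support that; they support only that the review as specified is not separated by arm. This part of the reply stands and sets the limit of the point.

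A reader might also infer that more intensive screening in FFT-MCC would show the board a spurious imbalance. Under the review as written, a table not split by arm could show no arm imbalance, true or false. Self-harm reports "either in voice samples or on daily or weekly questionnaires" do go to a study clinician, and daily ratings exist only in FFT-MCC. However, the daily items listed in Table 1 are mood, sleep, and perceived criticism and stress; no self-harm item is among them. Voice samples, the weekly PHQ-9, and the suicide measures at standard intervals follow the same schedule in both arms. Unequal detection is therefore a reason for care in building an arm table, not a demonstrated bias.

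It is also fair to say that phase is not wholly unrelated to the app, since full-app messages follow the therapy modules. Phase still does not separate the arms. Finally, the trial is small, rated minimal risk by the protocol and called exploratory by the SAP, and formal power is low. That limits what an arm table can prove. It does not justify leaving the randomised factor out of the stated review.

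**Conclusion.** The point holds in a limited form. The stated review uses an axis common to both arms, nothing elsewhere in either document adds one by arm, and the listed phases omit engagement and the last 9 of 27 weeks. The protocol's assertion that the fuller app adds no risk is therefore not checked by any planned safety review. This rests on reading the text and needs no numerical assumption.

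The numbers serve only to set expectations. At about 4 expected hospitalisations, which assumes that the 13% rate carries over to this sample and is constant over time, an arm table is for descriptive monitoring. A split such as 6 against 0 reaches p = 0.024, but it is a selected example and should not be read as what the trial could be expected to detect. Nothing in the documents is evidence that the app causes harm. The defect is modest and cheap to correct, and no efficacy estimate depends on it.

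**What to change.** Amend the Data Safety Monitoring Board sentence so that serious and other adverse events are reviewed by randomised arm as well as by treatment phase. The arm table would carry coded arm labels and be prepared by the study's biostatistics core. Extend the phase list to include engagement and weeks 18 to 27. Add an arm-level adverse event summary to the SAP.

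Base the arm table on events the independent evaluator records at weeks 9, 18 and 27, because that schedule is the same in both arms. An equal schedule does not guarantee equal reporting, so the table should state its source. List events first detected through the app separately, since app contact is more frequent in FFT-MCC. State that the table is descriptive, without a significance threshold.

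Restricting the PIs to figures not split by arm is not part of this fix. They report to the board, approve analysis datasets and usually serve as the clinician for flagged samples, so such a restriction would change roles well beyond this point.

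The cost is one extra table per board report and a short SAP addition. Sample size, assessments and clinical management are unchanged. The 2023 SAP is written in the past tense; if follow-up has ended, the part still usable is the arm-level summary in the final report, drawn from events already recorded.
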